Study Protocol and Statistical Analysis Plan:

Our study was designed as prospective cohort study. 65 women between the ages of 18-52 who applied to the Istanbul Medical Faculty Gynecology and Infertility departments due pelvic pain, infertility or abnormal bleeding between October 2018-October 2021 were included in the study. As a result of their gynecological examination and transvaginal ultrasonography results, these women were divided into adenomyosis (n=34) and fibroids (n=31) groups. Women with a history of malignancy, oral contraceptive use, hormonal intrauterine device users or women using gonadotropin-releasing hormone agonists were not included in the study. Ethical committee approval was given and informed consents were obtained from the patients before the examination.

The definitive diagnosis of patients with suspected adenomyosis and fibroids according to transvaginal ultrasound examination was confirmed by intravenous contrast-enhanced pelvic MRI. Thus the reference method used for confirmation was MRI. Magnetic resonance imaging was evaluated by a separate radiology specialist with 17 years of experience in pelvic MRI. If the junctional zone was observed to be thicker than 1.2 cm in magnetic resonance imaging, or the difference between the maximum and minimum measurement values taken from the junctional zone was more than 0.5 cm, adenomyosis diagnosis was established. Focal lesions with clear borders in the uterus were interpreted in favor of myoma uteri. (1)

In the study group, detailed anamnesis was taken from the patients, their menstrual cycles, body mass indexes, current drug use, family history, and smoking habit were questioned. The patients included in the study (adenomyosis group) and control group (fibroid group) were examined with both transvaginal ultrasound and transvaginal elastography devices.

Siemens Acuson X600 EV9F10 endovaginal ultrasound with 3-9 MHz frequency and 180 degree viewing angle probe was preferred for transvaginal ultrasound examination. Canon Applio i800 11C3 endovaginal ultrasound with 3-11 MHz frequency and 180 degree viewing angle probe was used for elastography examination.

Elastography data of the study and control groups were compared. Shear wave elastography was used with a transvaginal transducer providing a clear image up to 3 cm depth. No additional pressure or compression was applied to the transvaginal probe during the procedure. Minimum pressure was applied to the cervix for imaging and the probe was held still for approximately 2-5 seconds to obtain a fixed, stable image of the imaging field which contains the pathological lesion. The technique implemented in our study was adopted from the literature published by Mitkov et al. (2)(3)

Transvaginal gray scale ultrasound was performed in B-Mode by a gynecologist with at least 10 years of gynecological ultrasonography experience. In the study group, the presence/absence of hypoechoic areas, anechoic pools, asymmetric uterine growth, global uterine enlargement, deletion of the endo-myometrial zone, subendometrial thickening, global uterine growth, and linear shadows extending in the form of fans in the myometrium were recorded. Then, patients listed in study group were evaluated with elastography, and the hardness of the existing lesions was expressed in Young's modulus and recorded as elastographic data. Sonoelastography imaging was performed by an expert radiologist with 20 years of transabdominal/transvaginal ultrasonography and 7 years of sonoelastography experience.

To measure tissue stiffness in shear-wave elastography, Young's modulus, whose unit is kilopascal (kPa), was used in gynecological mode, with an upper limit of 180 kPa. Numerical values of Young's modulus were measured in areas with maximum myometrial stiffness for the respective pathologies. (Adenomyosis/Fibroid) Measurements were recorded on images in which the color window containing the lesion was completely stained and shear waves were completely set with equal distances over the pathological lesion in shear wave elastography. Tissue stiffness of the examined area was visualized with a color map in real-time mode. Harder tissues with high kPa values are mapped in red, green and yellow colors, while relatively soft tissues with lower kPa values are indicated in blue-violet colors. Evaluation of tissue stiffness was made in selected regions of interest with round-shaped circles adjustable up to 10 mm in diameter. All images and data were saved in the memory of the ultrasound device for further evaluation and processing. The

numerical values which represent the mean stiffness value of the region of interest; were set automatically in terms of kilopascal according to Young's Modulus by the device. These mean stiffness values were defined, and the minimum and maximum mean stiffness values were recorded for both study and control groups.

While evaluating the findings, IBM SPSS Statistics 22 program was used for statistical analysis. The conformity of the parameters to the normal distribution was evaluated with the Shapiro Wilks test. During the assessment of the study data, in addition to descriptive statistical methods (mean, standard deviation, minimum, maximum, median frequency), Student's t-test was used for comparisons between groups of normally distributed parameters and Mann Whitney U test was used for comparisons of non-normally distributed parameters between two groups. Fisher's Exact Chi-Square test, Fisher Freeman Halton Exact Chi-square test, Continuity (Yates) Correction and Mc Nemar test were used to compare qualitative data. Kappa coefficient of agreement was calculated for the level of agreement between MR diagnosis and transvaginal ultrasound. The most appropriate cut-off point was chosen based on the ROC curve analysis. Significance was evaluated at the $p < 0.05$ level.

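### The groups compared on stiffness are described as formed by examination and transvaginal ultrasound (TVUS) although MRI is the declared reference, and the handling of women on whom the two disagree is not stated

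*Combined protocol and SAP*

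**What the plan says.** The combined protocol and SAP has no section numbers, so places are given by paragraph.

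- **Grouping (opening paragraph).** "As a result of their gynecological examination and transvaginal ultrasonography results, these women were divided into adenomyosis (n=34) and fibroids (n=31) groups".
- **Reference standard (second paragraph).** "The definitive diagnosis of patients with suspected adenomyosis and fibroids according to transvaginal ultrasound examination was confirmed by intravenous contrast-enhanced pelvic MRI", followed by "Thus the reference method used for confirmation was MRI". Adenomyosis on MRI is defined by junctional zone thickness above 1.2 cm, or by a difference above 0.5 cm between its maximum and minimum. The fibroid criterion is separate: "Focal lesions with clear borders in the uterus were interpreted in favor of myoma uteri".
- **Names of the groups (third paragraph).** "The patients included in the study (adenomyosis group) and control group (fibroid group) were examined" with both devices. Study group means adenomyosis and control group means fibroid; neither is redefined by MRI.
- **Comparison (paragraph on the elastography technique).** "Elastography data of the study and control groups were compared". The measurement paragraph adds that stiffness was "measured in areas with maximum myometrial stiffness for the respective pathologies".
- **Statistical analysis (final paragraph of text).** Two-group tests are listed. A kappa is planned for MRI diagnosis against TVUS. A cut-off is to be chosen from a ROC curve, but neither the variable being cut nor the diagnosis that defines a positive case is named. McNemar's test is listed without its variables.

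**The concern.** A diagnostic study should judge the index test, here shear-wave stiffness, against its reference standard. This plan names MRI as that standard, but the one sentence that forms the groups relies on examination and TVUS. The later comparisons refer back to the groups by name only.

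The label decides what each stiffness result means. If it is TVUS, every woman whose MRI diagnosis differs sits in the wrong group relative to the declared reference. The stiffness difference then partly reflects agreement with ultrasound, and so does the apparent accuracy at the cut-off if the ROC analysis uses stiffness. If the label is MRI, the grouping sentence is wrong as written. As the text stands, two analysts with the same data could form different groups, and a reader could not tell which label was used.

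**Working it through.** **1. The plan's own figure.** 34 + 31 = 65, which matches the stated total. The documents give no discordance count, stiffness data or target accuracy, so the actual effect cannot be computed.

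**2. What the passages imply together.** Consider three possible meanings of 34/31.

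- *TVUS groups kept for analysis.* This is the literal reading. The reference standard then enters the kappa but not the stiffness results.
- *MRI groups.* Women were regrouped after MRI. The grouping sentence then does not describe the analysed groups.
- *Only women on whom TVUS and MRI agree.* Kappa in these 65 would be 1 by construction. A planned kappa is informative only if discordant women are among the 65, or if it uses a wider set that the text does not describe.

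No sentence selects among these.

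**3. Scale, errors unrelated to stiffness (illustration; all inputs except the group sizes are assumed).** AUC is used here only as a summary of the ROC curve; the plan does not name it. Take the TVUS margins 34/31, with k1 and k2 women in the two groups whose MRI diagnosis is the other condition. Let m1 = k1/34 and m2 = k2/31. Then:

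- observed mean difference = (1 − m1 − m2) × true difference
- observed AUC = 0.5 + (1 − m1 − m2) × (true AUC − 0.5)
- kappa = (po − pe)/(1 − pe). With k1 = k2 = k, po = (65 − 2k)/65 and pe = (34² + 31²)/65² = 2117/4225 = 0.501.

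For k = 1: m1 + m2 = 0.0294 + 0.0323 = 0.0617, so the factor is 0.938. Kappa = (0.9692 − 0.5011)/0.4989 = 0.938. A true AUC of 0.85 becomes 0.5 + 0.938 × 0.35 = 0.828.

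| Discordant women | Factor 1 − m1 − m2 | Kappa | AUC if truly 0.70 | if truly 0.85 | if truly 0.95 |
|---|---|---|---|---|---|
| 1 + 1 | 0.938 | 0.938 | 0.688 | 0.828 | 0.922 |
| 3 + 3 | 0.815 | 0.815 | 0.663 | 0.785 | 0.867 |
| 5 + 5 | 0.692 | 0.692 | 0.638 | 0.742 | 0.811 |

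One-way discordance is similar. Six of the 34 relabelled as fibroid gives MRI groups of 28/37, kappa 0.817 and AUC 0.5 + (1 − 6/34) × 0.35 = 0.788. Six of the 31 relabelled as adenomyosis gives 40/25, kappa 0.813 and AUC 0.782.

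In this setting the observed Youden index is (1 − m1 − m2) times the true one at every cut-off. The best cut-off therefore does not move on average; only its apparent accuracy falls.

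**4. Direction.** Attenuation is not guaranteed. A binormal simulation used a true AUC of 0.85, 400,000 per group, error rates averaging 5%, 10% or 20%, and a logistic dependence of error on stiffness with slope 1 or 2 per SD. If ultrasound misreads the women whose stiffness resembles the other condition, the observed AUC is 0.84 to 0.92. If it misreads those who resemble it least, the AUC is 0.54 to 0.78. The documents give no reason to prefer any of these settings. They show only that the sign is not known.

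**The case against.** The strongest reply is that the second paragraph describes a two-step process. Women were first divided on examination and ultrasound. They are then called suspected cases whose definitive diagnosis MRI confirmed. The grouping sentence does not exclude later confirmation and does not say that ultrasound labels were kept for analysis. This stands as a possible reading, so a reader should not infer that TVUS labels were in fact used or that any woman was misclassified. The documents establish only that the label is unclear, and that its literal wording points to TVUS.

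A reader might also take the order of examinations ("Then, patients listed in study group were evaluated with elastography", placed after the grey-scale findings) as evidence for TVUS labels. It is not: the timing of MRI is not given, and the order says nothing about which diagnosis was analysed.

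Discordance is also partly covered, because the planned kappa already requires the TVUS-by-MRI table, and McNemar's test might apply to the same pair. That narrows the gap without closing it: the women entering the table and the assignment of discordant women remain unstated.

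Finally, the illustrations rest on assumed inputs. They show that the label can matter, not that it did. The unnamed ROC test variable, and the absence of a rule for women meeting both or neither MRI definition, are reporting gaps. The second would remain even if MRI labels were declared.

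**Conclusion.** The point holds as a should-fix. As written, the stiffness comparison is between groups formed by examination and TVUS, while MRI is the declared reference and TVUS–MRI disagreement is treated as possible. The ROC cut-off has the same problem if it uses stiffness, which the design suggests but the text does not state.

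The bias is of unknown size and direction, and is zero if no woman was discordant. The fall in AUC from 0.85 to between 0.83 and 0.74 assumes 1 to 5 discordant women per group and errors unrelated to stiffness; neither assumption comes from the documents. Two stronger conclusions are not supported: that the reported accuracy must be too low, since stiffness-related errors can push it either way; and that the chosen cut-off must be wrong, since with unrelated errors a Youden cut-off stays in place on average.

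**What to change.** 1. Define the groups for every stiffness comparison, and the ROC state variable, by the MRI diagnosis already held. Amend the grouping sentence in the opening paragraph to match. If 34/31 are already the MRI-confirmed groups, one sentence saying so settles the label.
2. Report the TVUS-by-MRI table behind the kappa for all women who had both examinations.
3. State how many women were discordant, and how many met both or neither MRI definition, and say how each was assigned.
4. Optionally, add an analysis without relabelled women. It removes hard cases and has its own bias: in the step 4 simulation, a true AUC of 0.85 becomes 0.87 to 0.95 among concordant women if look-alike cases are the ones misread, and 0.78 to 0.84 in the opposite case.

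**Cost.** Wording, and possibly relabelling; no new scans, since the text describes the MRI examinations as done. Group sizes may differ from 34/31. In relabelled women the region of interest may have been placed on the lesion identified by TVUS, which relabelling cannot correct and which should be disclosed.

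### Does the lack of a rule for women who meet both MRI definitions undermine the kappa between MRI and transvaginal ultrasound?

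*Combined protocol and SAP*

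**What the plan says.** The second paragraph of the combined protocol and SAP makes MRI the standard: "Thus the reference method used for confirmation was MRI". It then gives two reading rules. Adenomyosis is diagnosed when the junctional zone exceeds 1.2 cm or when "the difference between the maximum and minimum measurement values taken from the junctional zone was more than 0.5 cm, adenomyosis diagnosis was established". For fibroids, "Focal lesions with clear borders in the uterus were interpreted in favor of myoma uteri".

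The first paragraph assigns women on gynecological examination and transvaginal ultrasound (TVUS): "these women were divided into adenomyosis (n=34) and fibroids (n=31) groups". The exclusions concern malignancy and hormonal treatment: "Women with a history of malignancy, oral contraceptive use, hormonal intrauterine device users or women using gonadotropin-releasing hormone agonists were not included". Having both diseases is not listed.

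The statistical paragraph says "Kappa coefficient of agreement was calculated for the level of agreement between MR diagnosis and transvaginal ultrasound". It does not list the categories of either variable. McNemar's test appears only in a general list ("Mc Nemar test were used to compare qualitative data"), with no variables named.

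**The concern.** The adenomyosis rule is a measurement on the uterus and the myoma rule describes a lesion. Neither is conditional on the other, so a woman with a thick junctional zone and a well-defined focal lesion satisfies both. The plan has two groups, no category for both diseases and no precedence rule.

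If the kappa uses one two-way MRI label per woman, each mixed woman has to be put on one side by a choice that the document does not record. MRI is the reference, so a reader will take kappa as a measure of how well TVUS identifies the disease. Some of the disagreement, or agreement, might instead reflect that labelling choice, and the two could not be told apart from the plan.

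**Working it through.** **Figures in the document.** The only relevant figure that can be checked is the total: 34 + 31 = 65, which matches. No kappa, no MRI-by-TVUS table and no count of mixed women is given, so what follows is an illustration under assumed counts.

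**Method.** Fix the TVUS margins at 34 (adenomyosis) and 31 (fibroid). Kappa = (po − pe)/(1 − pe), where po is the observed agreement and pe is the agreement expected from the margins.

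**Worked case: 6 mixed women, 3 in each TVUS group, all others agreeing.**

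- *Adenomyosis takes precedence.* The 3 mixed women in the fibroid group become discordant. MRI margins are 37 and 28; po = 62/65; pe = (34×37 + 31×28)/65² = 2126/4225. Kappa = (4030 − 2126)/(4225 − 2126) = 1904/2099 = 0.907.
- *Myoma takes precedence.* The 3 mixed women in the adenomyosis group become discordant. MRI margins are 31 and 34; po = 62/65; pe = (34×31 + 31×34)/65² = 2108/4225. Kappa = 1922/2117 = 0.908.
- *Label follows the TVUS group.* Kappa = 1.00.

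**Range of assumptions.**

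| Mixed women (TVUS adenomyosis/fibroid) | Other discordant women | Follows TVUS | Adenomyosis first | Myoma first | All against TVUS |
|---|---|---|---|---|---|
| 3 (2/1) | 0 | 1.00 | 0.969 | 0.939 | 0.908 |
| 6 (3/3) | 0 | 1.00 | 0.907 | 0.908 | 0.815 |
| 13 (7/6) | 0 | 1.00 | 0.813 | 0.786 | 0.600 |
| 3 (2/1) | 6 (3 each way) | 0.815 | 0.784 | 0.754 | 0.723 |
| 6 (3/3) | 6 (3 each way) | 0.815 | 0.721 | 0.724 | 0.630 |
| 13 (7/6) | 6 (3 each way) | 0.815 | 0.627 | 0.603 | 0.415 |

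With no mixed women, every rule gives the same kappa. The last column is not a realistic reading of the plan: a fixed precedence rule can contradict every mixed woman's TVUS group only if all of them sit in one group. Under a fixed rule and a near-even split, the direction of precedence moves kappa by at most 0.03 (0.969 − 0.939 = 0.030 in the first row; 0.813 − 0.786 = 0.027 in the third). The larger gap is between any fixed rule and labels that simply follow TVUS.

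**What else could depend on the label.** The elastography section compares the study and control groups, which the first paragraph forms from examination and TVUS. It takes stiffness at the site of the disease in question. As described, the MRI label does not enter that comparison. The plan does not say that the ROC analysis or McNemar's test uses the MRI label, so the point rests on kappa alone.

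**The case for a change.** The strongest case for acting is that the overlap is plain on the page and touches a named statistic. The myoma sentence says how to read a focal lesion. It does not say what the woman is called when her junctional zone also qualifies, and for that criterion the text speaks of an established diagnosis. If 13 of 65 women were mixed, a fixed rule would lower kappa by about 0.2 (1.00 − 0.813 = 0.19; 1.00 − 0.786 = 0.21). Recoding MRI reads already made would need no new imaging.

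The overlap and the silence on categories stand. The rest is weaker. The counts of 3, 6 and 13 have no source in the document, and 13 of 65 supposes that 20% of the women had both diseases. The two MRI sentences are adjacent and read as a differential diagnosis: junctional-zone change points one way, a well-defined focal lesion the other, with one diagnosis per woman. That reading is not explicit, but it is reasonable.

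Adding analyses would also gain little. TVUS supplies a single group per woman, so counting mixed women first as adenomyosis and then as myoma makes some of them discordant by construction. The result is a pair of bounds and not a better measure of TVUS accuracy. Separate kappas per disease would need both diseases recorded by TVUS in every woman, whereas the adenomyosis features are described for one group only ("In the study group, the presence/absence of hypoechoic areas, anechoic pools, asymmetric uterine growth"). Moving women between arms in the elastography analysis could put stiffness measured in a fibroid into the adenomyosis arm, or the reverse.

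**Conclusion.** This is a missing detail that analysts can fill sensibly, and no change to the plan follows. The two MRI rules can overlap and the label for a woman who meets both is unwritten. However, no such woman is shown to exist, a one-diagnosis reading is available, and no stated rule is shown to give a wrong kappa. The effect is unknown and is zero if there were no mixed women. With a few (3 or 6), otherwise perfect agreement, a fixed precedence rule and a near-even split, kappa would lie between about 0.91 and 0.97 instead of 1.00. Those values depend entirely on the assumed counts.

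The text is written in the past tense with group sizes already fixed, so what remains belongs to the reporting of results: the label used, the number of women who met both rules and the MRI-by-TVUS table would let a reader judge the kappa.

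### Does leaving the analysed stiffness value unnamed undermine the group comparison and the ROC cut-off?

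*Combined protocol and SAP*

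**What the plan says.** The document has no section headings, so I refer to its paragraphs by subject.

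- Elastography examination: "Then, patients listed in study group were evaluated with elastography, and the hardness of the existing lesions was expressed in Young's modulus". The comparison itself is stated only as "Elastography data of the study and control groups were compared".
- Position of the measurement: "Numerical values of Young's modulus were measured in areas with maximum myometrial stiffness for the respective pathologies".
- Region: "Evaluation of tissue stiffness was made in selected regions of interest with round-shaped circles adjustable up to 10 mm in diameter". The colour window over the lesion had to be fully stained. No number of regions per woman or per lesion is given.
- Value read from each region: the device supplies "numerical values which represent the mean stiffness value of the region of interest", in kPa.
- Recording: "These mean stiffness values were defined, and the minimum and maximum mean stiffness values were recorded for both study and control groups".
- Statistics: minimum and maximum appear in the list of descriptive statistics. Student's t-test or the Mann-Whitney test is applied to parameters that are not named. For the cut-off: "The most appropriate cut-off point was chosen based on the ROC curve analysis". Neither the marker nor the selection criterion is named; that the marker is stiffness is an inference.
- Storage: "All images and data were saved in the memory of the ultrasound device for further evaluation and processing".

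**The concern.** Stiffness is the main measurement of the study, and at least four per-woman values fit the text: a single stiffest-area reading, a maximum over regions, a minimum, or an average. The measurement paragraph points to the stiffest area, while the recording sentence mentions both extremes, so the two can look inconsistent.

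Extremes depend on how many readings they are taken over. More regions raise a maximum and lower a minimum. Adenomyosis and fibroids may differ in extent and in internal variation, so region number or spread could differ by group. Two analysts could then obtain opposite differences and different kPa cut-offs from the same women. An unnamed value also leaves room to choose after seeing the results, and a cut-off is hard to apply elsewhere if the reader does not know what was measured.

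**Working it through.** The plan gives no SD, effect size, power or region count, so there is no figure of its own to reproduce. From the document I take the group sizes (34 + 31 = 65), the 0.05 level (two-sided assumed) and the stiffest-area rule. Region numbers, spread and correlation are assumptions.

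**Model.** Each woman has her own level with variance ρ. Each region adds an independent normal deviation with variance 1 − ρ. I use ρ = 0.5/0.7/0.9, equal true means and a two-sample t-test. Shifts are in pooled SDs of the recorded value.

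**Step 1: regions placed at random.** The expected maximum of k standard normal values is 0.846 for k = 3, 1.267 for k = 6 and 1.539 for k = 10; the expected minimum is its negative. For 6 against 3 regions at ρ = 0.5, the raw shift is √0.5 × (1.267 − 0.846) = 0.707 × 0.421 = 0.298. Dividing by the pooled SD of the maxima gives 0.35.

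| Random placement | Maximum (minimum is the mirror image) | p<0.05 by maximum | Average |
|---|---|---|---|
| 6 vs 3 regions | +0.35/+0.25/+0.14 | 28%/17%/9% | 0.00, about 5% |
| 10 vs 3 regions | +0.58/+0.42/+0.23 | 63%/38%/15% | 0.00, about 5% |
| 3 vs 3, 1.5 times the within-lesion SD in one group | about +0.30/+0.23/+0.13 | 23%/15%/8% | 0.00, about 5% |

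In this model the extremes move in opposite directions and the average is safe.

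**Step 2: regions placed by the plan's rule.** The operator reads where the live colour map is stiffest. I represent this by taking the top k of 20 candidate sites; 20 is an assumption.

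| Stiffest of 20 sites | Maximum | Average | p<0.05 by average |
|---|---|---|---|
| 6 vs 3 regions | 0.00, about 5% | −0.34/−0.23/−0.12 | 28%/15%/8% |
| 10 vs 3 regions | 0.00, about 5% | −0.66/−0.45/−0.23 | 75%/43%/15% |
| 3 vs 3, 1.5 times the SD | +0.77/+0.56/+0.30 | +0.66/+0.46/+0.24 | 75%/44%/16% |

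The maximum no longer depends on the number of regions, because the stiffest site is read in every woman. The average falls as more, and therefore softer, sites are added. In the last row the minimum also rises (+0.52/+0.35/+0.19), in the same direction as the maximum. With imperfect targeting (selection noise equal to the within-lesion SD) and 6 against 3 regions, the maximum moves by +0.10/+0.07/+0.04 and the average by −0.23/−0.16/−0.09.

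**Step 3: one reading per woman.** If the recorded minimum and maximum are the range across women in each group, each woman contributes one stiffest-area value. Minimum, maximum and average then coincide and there is nothing to choose between.

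**Step 4: testing both extremes.** With 3 regions per woman, equal spread, random placement and no true difference, at least one of minimum and maximum has p<0.05 in 8.3%/7.4%/6.7%.

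**The case for a change.** The strongest case for acting is that the plan does not define its central variable. A published kPa threshold means little unless the reader knows whether it refers to one reading, a maximum or an average. The stiffest-area rule makes the maximum the natural reading, but the plan does not say so. The group-range reading leaves the region count unstated. The technique is said to be adopted from cited papers, which I have not seen. The images were saved, so settling the matter would cost one definition and one rerun on 65 women.

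Most of that stands as a comment on completeness: the report of results should say what was measured. It does not show that the analysis is wrong. Harm requires several regions per woman, numbers or spread that differ by group, and an analysed value sensitive to that difference. The document supports none of the three. Averaging all recorded regions, the remedy that looks safest, would bring in a dependence on region number under the plan's own placement rule, where the maximum has little or none. Re-placing regions on saved images would add reading work to correct an imbalance that nobody has shown.

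**Conclusion.** No change to the plan follows. The per-woman value and the region count are not written down, but the stiffest-area rule leads an analyst to a single stiffest-area reading or the maximum, used for both the comparison and the ROC. The recorded minimum and maximum can be read as group ranges, so the apparent conflict is possible rather than established.

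On that reading, unequal region numbers shift the result by nothing under exact targeting and by at most 0.10 SD in the imperfect-targeting case. If within-lesion spread differs, the maximum does move, but that is a real difference in peak stiffness, which is what the plan sets out to measure. The larger shifts, and the opposite movement of minimum and maximum, need random placement or a different summary.

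All sizes rest on assumed region numbers, correlations, normal values and 20 candidate sites. The direction of any effect depends on how regions were placed, so these figures do not estimate bias in this study. I would think differently if the data showed several regions per woman with clearly unequal numbers by group and a minimum or an average as the analysed value.

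### MRI is declared the reference method, but the only statistic named for transvaginal ultrasound against it is kappa, which cannot show whether ultrasound misses or over-calls adenomyosis

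*Combined protocol and SAP*

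**What the plan says.** The document has no numbered sections, so places are given by paragraph.

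- **Study population (opening paragraph).** The study included "65 women between the ages of 18-52". On the basis of gynaecological examination and TVUS, "these women were divided into adenomyosis (n=34) and fibroids (n=31) groups". Read literally, 34 and 31 are totals of the ultrasound classification.
- **MRI confirmation (second paragraph).** Diagnoses suspected on TVUS were confirmed by contrast-enhanced pelvic MRI: "Thus the reference method used for confirmation was MRI".
- **Statistical paragraph (before the references), TVUS against MRI.** "Kappa coefficient of agreement was calculated for the level of agreement between MR diagnosis and transvaginal ultrasound". No other statistic is assigned to this comparison.
- **Same paragraph, general list of tests.** "Continuity (Yates) Correction and Mc Nemar test were used to compare qualitative data". The list does not say which comparison McNemar serves.
- **Same paragraph, ROC.** "The most appropriate cut-off point was chosen based on the ROC curve analysis". The variable is not named. It is presumably the elastography stiffness value, and a cut-off has no bearing on a binary TVUS diagnosis.

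Sensitivity, specificity, predictive values and confidence intervals are not mentioned anywhere in the document.

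**The concern.** Once one method is declared the reference, the natural questions about the other are directional. How often does it miss the condition, and how often does it call the condition when it is absent? Kappa answers a different question: how far two raters of equal standing agree beyond chance. Swapping the roles of TVUS and MRI leaves it unchanged.

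A report built on kappa alone would give one agreement figure for TVUS, and readers could not tell from it whether ultrasound tends to label fibroids as adenomyosis or the reverse. With 65 women the figure is also imprecise, and the plan does not commit to showing how imprecise.

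**Working it through.** **Is there a figure to reproduce?** No. The document gives no kappa value, no TVUS-by-MRI table and no sample-size calculation. The only arithmetic available is 34 + 31 = 65, which agrees.

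**Inputs.** From the document: TVUS adenomyosis 34, TVUS fibroid 31, n = 65. Assumed: 8 disagreements with MRI, split three ways, with 4 and 12 as a range. A false positive (FP) is TVUS adenomyosis with MRI fibroid. A false negative (FN) is the reverse. Then TP = 34 − FP and TN = 31 − FN.

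**Kappa.** κ = (po − pe)/(1 − pe), where po = (TP + TN)/65 and pe = [34 × (TP + FN) + 31 × (TN + FP)]/65². With 8 disagreements po = 57/65 = 0.8769 throughout.

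- 8 FP, 0 FN: MRI totals 26 and 39. pe = (34×26 + 31×39)/4225 = 2093/4225 = 0.4954. κ = 0.3815/0.5046 = 0.756.
- 4 FP, 4 FN: MRI totals 34 and 31. pe = (34×34 + 31×31)/4225 = 2117/4225 = 0.5011. κ = 0.3759/0.4989 = 0.753.
- 0 FP, 8 FN: MRI totals 42 and 23. pe = (34×42 + 31×23)/4225 = 2141/4225 = 0.5067. κ = 0.3702/0.4933 = 0.750.

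**Accuracy from the same tables.** Sensitivity = TP/(TP + FN); specificity = TN/(TN + FP); PPV = TP/34; NPV = TN/31. Intervals are Clopper-Pearson for proportions and large-sample (Fleiss-Cohen-Everitt standard error) for kappa.

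| FP/FN | Kappa (95% CI) | Sensitivity (95% CI) | Specificity (95% CI) | PPV | NPV |
|---|---|---|---|---|---|
| 8/0 | 0.756 (0.603–0.910) | 26/26 = 100% (86.8–100) | 31/39 = 79.5% (63.5–90.7) | 76.5% | 100% |
| 4/4 | 0.753 (0.593–0.913) | 30/34 = 88.2% (72.5–96.7) | 27/31 = 87.1% (70.2–96.4) | 88.2% | 87.1% |
| 0/8 | 0.750 (0.594–0.907) | 34/42 = 81.0% (65.9–91.4) | 23/23 = 100% (85.2–100) | 100% | 74.2% |

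Kappa moves by 0.006 while sensitivity moves by 19 percentage points and specificity by about 20. The kappa intervals are 0.307, 0.320 and 0.313 wide.

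**Range of the assumption.** With 4 disagreements kappa is 0.876 to 0.877, sensitivity 89.5% to 100% and specificity 88.6% to 100%; the kappa interval is about 0.23 wide. With 12, kappa is 0.624 to 0.636, sensitivity 73.9% to 100% and specificity 72.1% to 100%; the interval is up to 0.38 wide.

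**If McNemar was applied here.** The exact two-sided p-value depends only on the two error counts. For 8/0 and 0/8 it is 2 × 0.5⁸ = 0.0078. For 4/4 it is 1.00. It therefore separates balanced from one-sided errors, but the same p-value arises for opposite directions. For 7/1 and 1/7, p = 2 × (1 + 8)/256 = 0.070 in both, with kappa 0.755 and 0.751. Sensitivity is 27/28 = 96.4% against 33/40 = 82.5%, and specificity 30/37 = 81.1% against 24/25 = 96.0%. In no case does McNemar give an error rate.

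**If 34 and 31 are the MRI-confirmed counts instead.** The table is transposed. Kappa and McNemar are unchanged, and sensitivity and specificity exchange places with PPV and NPV. The 8/0 row would then read 76.5% and 100%, and the 0/8 row 100% and 74.2%. The conclusion is the same on either reading.

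**The case against.** **Kappa is a legitimate measure of agreement, and agreement is all that the sentence claims.** This is true, and TVUS against MRI is one sentence in a plan centred on elastography. It lowers the weight of the point. It does not remove it, because the document itself gives MRI the status of reference, and a symmetric statistic ignores that status.

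**The design may not support accuracy estimates.** Every woman entered on a TVUS suspicion of one of two conditions, and there is no disease-free group. Sensitivity and specificity would describe only how TVUS separates adenomyosis from fibroid among suspected women, not how well it detects disease. If only women with confirmed diagnoses were kept, the table is diagonal by construction. Nor do the documents say that unconfirmed women were recorded, or how MRI showing both conditions was classified. All this stands as a limit on the fix, but kappa has the same limits: it needs the same paired diagnoses and is equally uninformative if disagreements were excluded.

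**Stronger readings that the documents do not support.**

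- A reader might infer that kappa and McNemar together hide every difference in error pattern. McNemar is not tied to this comparison, and elastography classified at its cut-off against MRI would also be paired binary data. If McNemar was used for TVUS, it would flag one-sided errors, as shown above; only mirror-image patterns share both statistics.
- A reader might treat 34 and 31 as MRI totals and take 34/34 and 21/31 as sensitivity 100% and specificity 68%. The opening paragraph forms the groups from examination and TVUS. With those as TVUS totals, the same counts give sensitivity 34/44 = 77% and specificity 100%, the opposite pattern. For the same reason 34:31 is not an MRI prevalence.
- A reader might say that the plan excludes an interval for kappa. It is silent on intervals.

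**Conclusion.** The point holds as a shortcoming in the choice of analysis for TVUS against MRI. The named statistic does not identify the direction of ultrasound errors. At 8 assumed disagreements in 65 women, a kappa of about 0.75 is compatible with sensitivity from 81% to 100% and specificity from 79% to 100%.

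The conclusion rests on the absence of any accuracy measure from the text, and on the symmetry of kappa, which needs no data. The sizes rest on assumed disagreement counts and on 34/31 as TVUS totals. The elastography comparison between groups is not affected. It is something the sponsor should change, not a fault that undermines the study.

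**What to change.** 1. Report the TVUS-by-MRI 2x2 table for all women who had both examinations, including those whose MRI did not confirm the TVUS call. State how women with both conditions, or neither, on MRI were counted.
2. From it, give sensitivity, specificity, PPV and NPV for adenomyosis versus fibroid with exact 95% confidence intervals, stated as conditional on TVUS suspicion.
3. Keep kappa as a secondary measure with its 95% confidence interval.
4. State which comparison McNemar serves. If it is TVUS against MRI, report it as a test of balance between the two kinds of error and draw no conclusion about accuracy from it.
5. If only MRI-confirmed women were retained, state that neither agreement nor accuracy of TVUS can be estimated.

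The cost is one extra table and a few sentences in the SAP, built on the paired diagnoses that kappa already requires. Whether unconfirmed women were recorded is not stated and must be checked first. The downside is that the reported precision will look less favourable: in the illustration the lower limits for sensitivity and specificity run from 63.5% to 86.8%.
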